5.4 SUBJECT PROCEDURES

5.4.1 SCREENING/ENROLLMENT/RANDOMIZATION

Activity	Screen	Enroll	Randomize
Interview, focus groups of clinicians	Invite all clinicians in Primary Care and Cardiology	Consent clinicians via Outlook/Teams	N/A
Questionnaires	Invite all clinicians who received nudges	Study Coordinator will send an email. (waiver of documentation of consent request)	N/A
Veterans and Family Advisory Council	Invite all Council members at scheduled Council meeting to participate	Interested Council members will verbally indicate consent to proceed with focus group	N/A
Deliver nudges (CPRS alerts and peer comparison emails) to clinicians	Study coordinator will identify eligible HF patient encounters (see inclusion/exclusion above)	Study coordinator will deliver nudge based on assigned nudge group (waiver of consent request)	VA Redcap will be utilized to randomly assign each clinician to nudge type (alert, email)

5.4.2 SUBJECT EVALUATIONS

Aim 1.

Subject	Data	Data source
Clinician	Verbal feedback: nudge intervention, workflow Quantitative measures of intervention suitability: questionnaires (Acceptability, Appropriateness, Feasibility) & Clinician general demographics: sex, practice site, specialty/subspecialty, and percent full-time effort, years of experience	Interview, focus group (see attached Interview Guides) Questionnaires (administered via VA Redcap)
Veteran and Family Advisory Panel	Feedback on intervention, workflow	Focus Group

Aim 2.

Subject	Data	Data source
Patient (12 months before baseline, during and post-nudge)	Name, full SSN, dates, demographics, vitals, zip-code level median household income, clinical encounters, Charlson Comorbidity Index, and medications; # alerts delivered, # new HF prescriptions (MRA or SGLT2), # HF	CPRS, HF Dashboard, CDW/VINCI

	medication discontinuations, adverse events, mortality	
--	--	--

5.4.3 FOLLOW-UP PROCEDURES

None

5.5 WITHDRAWAL OF SUBJECTS

Aim 1. PROCESS EVALUATION. The clinician or Veteran Advisory Council member has a right to withdraw from the interview, questionnaire, and/or focus groups. The subject withdrawal will occur either by stopping the interview/questionnaire or leaving the focus group. The data collected prior to the subject withdrawing will be used for the study. The data will be maintained in accordance with the Records Control Standards RCS-10.

Aim 2. NUDGE EFFECTIVENESS.
N/A - Waiver of consent requested.

5.6 SUBJECT COMPENSATION/COSTS

There is no compensation nor costs incurred by clinicians to participate in this study.

5.7 DATA COLLECTION

Aim 1. PROCESS EVALUATION

Data will be collected via note taking (Veteran and Family Advisory Panel) and audio recording (Clinicians). Note taking will occur during the Veteran and Family Advisory Panel. The study team taking notes will not collect and PHI/PII. The recordings will be performed via MS Teams. The completed interview or focus group's audio files will be immediately downloaded to the VA secured project folder and then deleted from where it is initially held (MS Stream). Audio transcripts will be analyzed using Atlas.ti located behind VA firewall. The MS Teams transcript will immediately be deidentified by the study team member, as MS Teams utilizes the name of the person speaking, downloaded to the VA study folder and deleted from the Teams site. The audio and transcripts will be maintain/destroyed in accordance with RCS 10-1. We are not collecting data on drug or alcohol abuse, sickle cell anemia and/or HIV status.

The audio files and transcripts will be stored behind two password protected firewalls for which only the study team will have access to at the SAVAHCS.

R:\Research_Investigator_Projects\Medicine\[name]\Nudge Study\

After the Nudge intervention, all clinicians who received nudges will receive email link to VA REDCap to complete <5 minute validated questionnaire about nudge intervention Acceptability, Feasibility and Appropriateness.

Aim 2. NUDGE EFFECTIVENESS

Data will be collected from one or more of: CDW/VINCI, PBM HF Dashboard, CPRS and stored in within the VA secured project folder utilizing MS Excel and VA Redcap databases. The study folder is restricted to IRB study team members. CDW/VINCI data will always reside within VINCI.

6.0 RISKS/BENEFITS

6.1 RISKS

AIM 1. PROCESS EVALUATION

Interviews and focus groups: Risks to clinicians and Veteran Advisory council are minimal because we are asking questions about a nudge intervention and not personal or sensitive matters. We are not asking questions related to PHI or PII.

AIM 2. NUDGE EFFECTIVENESS. Risks to subjects (clinicians) are minimal given the benign nature of this behavioral intervention, which recommends guideline-driven prescribing. Though clinicians are the recipient of the study interventions, it is worth noting that patient risks are also minimal because clinician prescribing behavior (or lack of prescribing) reflects their best professional judgment for that specific patient.

There is small risk of loss of privacy and confidentiality to clinicians and patients; see risk mitigation statement below in 6.3.

6.2 BENEFITS

Clinicians. There are no direct benefits of study participation. However, the study may contribute to generalizable knowledge about using nudges to improve quality of care. In addition, clinicians might increase his/her knowledge regarding HF treatment and be prompted to improve their HF prescribing practices.

Patients. There is no direct benefit. However, there is a potential benefit to patients if they are prescribed a recommended HF medication that otherwise would not have been prescribed without the study intervention.

6.3 RISK/BENEFIT ASSESSMENT

AIM 1. PROCESS EVALUATION

Interviews and focus groups: The potential risks of discomfort will be minimized by allowing the subject to skip any question or to stop the interview. Further, we are asking questions about a nudge intervention and not personal or sensitive matters. There is no risk to providers should they choose not to participate as this project will not affect his/her employment e.g., performance evaluation, pay, nor standing. Therefore, we believe the potential benefit to generalizable knowledge is greater than the risk. Any potential loss of privacy and confidentiality to clinicians is minimized by following all VA recommended practices (see Section 9.0 for detail).

AIM 2. NUDGE EFFECTIVENESS. Risks to subjects (clinicians) and their patients are minimal given the benign nature of this behavioral intervention recommending guideline-

driven prescribing which is common in routine clinical practice (e.g. EMR reminders). We believe the potential benefits to generalizable knowledge exceeds the risk. Any potential loss of privacy and confidentiality to patients is minimized by following all VA recommended practices (see Section 9.0 for detail).

7.0 DATA MONITORING FOR SUBJECT SAFETY

Aim 1. PROCESS EVALUATION. There is no data monitoring for clinician and Veteran Advisory Council members subject safety as this is a study regarding work practices and is minimal risk to the clinicians.

Aim 2. NUDGE EFFECTIVENESS. These are not experimental therapies, and DSMB is not required. SGLT2 inhibitors and MRAs are HF medications prescribed in routine standard of care and are guideline-recommended.

8.0 DATA ANALYSIS & STATISTICAL CONSIDERATIONS

Power calculation. One study reported a 14% absolute increase in beta-blocker prescription with enhanced alert compared to usual alert/usual care. Another reported a 7% absolute increase in new prescription of any GDMT in 30 days, also driven by beta-blocker. We anticipate a 5% absolute increase in new prescriptions (SGLT2 or MRA) per intervention arm, compared to usual care. We are anticipating a lower treatment effect because SGLT2 inhibitors are newer, potentially seen as requiring interdisciplinary collaboration, and MRAs require serial lab monitoring. To detect this difference with an 80% power and alpha of 0.05, a sample size of 168 patients who are eligible to activate the alert are required in each treatment group, for a total study sample size of 672 patients encounters. We anticipate that we can achieve this number of patient encounters across the approximately sixty participating clinicians including any possible attrition.

Data Analysis. Though randomization occurs at the clinician level, we will measure outcomes at the patient level. The dataset used for analysis will be limited to all MRA- and SGLT2i-eligible identified in the HF dashboard (this includes patients in the control group-- even though no alert will be generated). This sample allows us to compare differences in rate of prescription of the same patient types between the three intervention groups and control group. Descriptive statistics will comprise patient and provider demographics, including practitioner specialty and type, and part-time status. General Linear Models (GLM) and chi square tests will be used to compare continuous and categorical demographic variables, respectively, between the three interventions and control groups. Significant differences will be defined with p values < 0.05. Generalized Linear Mixed Models (GLMM) will be used to compare rates of both SGLT2 or MRA (in separate, univariate analyses) between the nudge intervention and control groups. Practitioner specialty and type, part time status, years of experience, and patient visit number will be included as covariates, and the patient, clinician, and clinic assignment (clustering of providers), will be entered as random effects. While these covariates are strata for randomization, it is unlikely, due to the study sample size, that all combinations will be equally distributed between the two groups. We will therefore need to employ statistical control of these potential influences. The GLMMs will be specified as random coefficient models or growth curve models to evaluate changes in prescription behavior over time, as well as between groups. Models will include the preintervention baseline as a covariate and will use all patient visits until the conclusion of the data collection period. Significant differences will be concluded with odds ratio and 95% confidence intervals that do not contain the value 1.0. This statistical approach

permits the evaluation of prescription rates by groups while controlling for covariates and the correlated and hierarchical effects of repeated measures nested within clusters. Statistical significance of the treatment group and the other covariates will be determined using odds ratio with 95% confidence intervals that do not contain 1.0. For the Secondary RE-AIM Outcomes, the GLMM, with the same random effects specification, will be used to estimate the safety risk for prescriptions of SGLT2 and MRA within 30 days of the nudge interventions and compare this risk between the intervention and control groups. These metrics will be evaluated to estimate the risk of discontinuation of the prescribed medications based on adverse effects. The outcome for this analysis will be the continuation or stoppage of the prescribed medication. The other metrics identified in the secondary outcomes above will be calculated as descriptive statistics and will inform revisions to the interventions.

Qualitative Analysis: To ensure analytic rigor, all analysts have experience in qualitative methods. Data collection and analysis will be conducted concurrently using deductive and inductive content analysis. Transcripts will be uploaded to ATLAS.ti for coding and data management. Coding is conducted using audio recordings and transcriptions simultaneously to ensure transcription fidelity and capture participant inflection not contained in transcript. Deductive content analysis consists of identifying quotes and phrases that fit within pre-identified and defined a-priori categories. A-priori categories include general behavioral economics principles, prism, RE-AIM domains. Inductive content analysis involves open/unstructured coding, and allows for the identification of emergent, previously unidentified and to capture data that did not fit into a-priori categories. For open coding, we will use a three-step process described by Strauss and Corbin to code the data, starting with open codes, followed by axial codes, and ending with theoretical codes (Strauss & Corbin, 1998). Coding will continue until thematic saturation (Sandelowski, 1995).

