1.0 BACKGROUND

Cognitive biases (Cheng, et al., 2021) can lead to irrational decisions. Nudge theory exploits cognitive biases in rejecting the assumption that humans will make optimal choices when given access to the right information. Based on nudge theory, interventions have provided support for decision making on how to save for retirement and whether to donate an organ. **Nudge theory also offers novel solutions to improve decision making in health care** (Lamprell, Tran, Arnolda, & Braithwaite, 2021). Nudges present **subtle changes in the decision-making environment** that can influence behavior by exploiting cognitive biases without significantly restricting choice (Lamprell, Tran, Arnolda, & Braithwaite, 2021). Nudges can range from most restrictive (e.g., opt-out) to minimally restrictive (e.g., providing information). This project will test the use of nudges to influence providers' prescribing behavior.

Gaps in VA heart failure (HF) prescribing practices provide an opportunity to test the effectiveness of nudges to improve decision making for prescribing heart failure medications. Of VA patients with HF with reduced ejection fraction (HFrEF) only 22% of eligible patients are receiving SGLT2 inhibitors and only 39% are receiving MRAs (U.S. Department of Veterans Affairs, 2022); despite clinical effectiveness, clinical inertia and barriers have prevented greater adoption of these two foundational therapies. In this proposed study, we will evaluate two nudge interventions, **informational alerts (in CPRS) and peer comparison feedback emails**, to improve HF prescribing.

Prior experience: Our group has previously reported HF prescribing barriers for VA clinicians ([name], et al., 2016), and we believe that the strategies in this proposal will overcome these barriers. Provider-based barriers to MRA prescribing include unclear provider roles/responsibilities, difficulties coordinating care, and lack of knowledge/experience with the drug ([name], et al., 2016). Two small studies suggest that SGLT2 barriers are similar; cardiologists reported barriers to prescribing SGLT2s including potential adverse effects (hypoglycemia, urogenital infections), lack of knowledge/skills with drug, concerns about managing diabetes, and concerns of professional roles (perceived SGLT2 as outside their scope of responsibilities) (Cheng, et al., 2021) (Gao, Peterson, & Pagidipati, 2020).

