Preliminary data: Informational alerts and peer comparison nudges have proven effective in other studies to change behavior. The PROMPT HF trial done in a university medical center demonstrated that informational alerts were associated with an increase in the number of GDMT medication classes prescribed (primary endpoint) from 19% to 26% ($p=.03$). One study compared individual audit feedback, peer comparison, and the combination, in a four-group design to influence clinician opioid prescribing in emergency care sites. They found a significant decrease in pills per prescription in the peer comparison arms.

We lack adequate knowledge about how to improve HF prescribing with nudges. Despite promising initial studies on the value of information alerts to improve HF prescribing, the improvements in prescribing were seen exclusively with beta-blockers, not in prescribing of SGLT2 inhibitors and MRAs – where the largest gaps exist in VA.

We need more information on whether combining nudges into multicomponent interventions is more effective.

A systematic review reported that only five of 48 nudge (10%) interventions in the literature were multicomponent; none of the studies were performed in the VA. For example, an evaluation active choice patient dashboard (delivered by email) with and without peer comparison to increase statin prescribing amongst PCPs found that only the active choice plus the peer comparison arm was associated with increased statin prescribing but not the active choice or the usual care arm alone. However, in these multicomponent trials, it is not clear which component is most impactful. Comparative effectiveness nudge trials are needed due to relative advantages and potential tradeoffs of each intervention. Further, research is needed to how nudges interact with one another and whether they may crowd each other out. In this proposal, we will evaluate whether informational alerts, peer comparison, or the combination of the two, is most effective.

This research will generate comparative evidence on which types and combinations of behavioral nudges work best. This study targets an HF treatment gap (SGLT2 and MRA) in which no prior nudge studies have demonstrated efficacy.

Our target population is clinicians in primary care and cardiology who are the main clinicians who treat HF. To incorporate the voice of the Veteran, we will meet with Veteran and Family Advisory Panel at SAVAHCS for feedback on the study design.

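### The 80% power claimed for 168 patients per arm is unsupported: no usual-care rate or ICC is stated, and the figure holds only at a very low rate with no clustering

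*Combined protocol and SAP*

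**What the plan says.** The power paragraph of section 8.0 sets the effect: "We anticipate a 5% absolute increase in new prescriptions (SGLT2 or MRA) per intervention arm, compared to usual care". It then claims this is detectable "with an 80% power and alpha of 0.05, a sample size of 168 patients" in each of four groups, for 672 patient encounters in all, to be drawn from "approximately sixty participating clinicians". It gives no usual-care rate of new prescribing, no sidedness, no test, no ICC or design effect, and no attrition rate.

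The data analysis paragraph of the same section states the design: "Though randomization occurs at the clinician level, we will measure outcomes at the patient level". Patient, clinician and clinic enter the mixed model as random effects. The decision rule is: "Significant differences will be concluded with odds ratio and 95% confidence intervals that do not contain the value 1.0".

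Other sections give three figures that bear on the point:
- Section 1.0 (preliminary data) cites an alert trial with an increase in "medication classes prescribed (primary endpoint) from 19% to 26" per cent.
- Section 1.0 reports current use: "only 22% of eligible patients are receiving SGLT2 inhibitors and only 39% are receiving MRAs".
- The table in section 4.2 lists 1,400 heart failure patients for analysis.

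**The concern.** An absolute difference between two proportions cannot be powered without the control proportion, because the variance depends on it. The paragraph omits it. The sample size of 168 is also small for a 5-point difference, which suggests either a control rate close to zero or an unusual calculation. Clinicians are the randomised units, so outcomes of patients under one clinician are likely to be correlated. The analysis model allows for this; the sample size shows no matching allowance.

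This is the plan's only justification of its size. Section 5.2 argues that learning that clinicians do not respond to nudges would spare the VA wasted scale-up efforts. A null result can support that use only if the stated power is sound.

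**Working it through.** **Inputs from section 8.0.** Difference 0.05, power 80%, alpha 0.05, 168 per arm, 4 × 168 = 672, about 60 clinicians. Two-sided testing is inferred from the 95% interval rule. The usual-care rate p0 and the ICC are not given, so ranges are shown.

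**Step 1: reproduce 168.** With p1 = p0 + 0.05 and p̄ = (p0 + p1)/2, the pooled two-sided formula is

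n = [1.96 √(2p̄(1−p̄)) + 0.8416 √(p0(1−p0) + p1(1−p1))]² / 0.05².

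Solving for n = 168 gives p0 = 0.27%. Check: p0 = 0.0027, p1 = 0.0527, p̄ = 0.0277, so n = (1.96 × 0.2321 + 0.8416 × 0.2294)² / 0.0025 = 0.4198 / 0.0025 = 168.

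Usual-care rate at which 168 per arm gives 80% power, for one arm against usual care and independent patients:

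| Test | Two-sided | One-sided |
|---|---|---|
| Pooled | 0.27% | 1.0% |
| Unpooled | 0.32% | 1.1% |
| Arcsine | 0.8% | 1.5% |
| Continuity-corrected | none (190 needed even at 0%) | 0.2% |

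**Step 2: power with 168 per arm, no clustering** (pooled, two-sided):

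power = Φ{[0.05 √168 − 1.96 √(2p̄(1−p̄))] / √(p0(1−p0) + p1(1−p1))}.

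At p0 = 5%: (0.6481 − 0.7301) / 0.3708 = −0.221, so power is 41%.

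| Usual-care rate | Power, 168 per arm | n per arm for 80% |
|---|---|---|
| 1% | 71% (70.5) | 211 |
| 2% | 60% | 269 |
| 5% | 41% | 435 |
| 10% | 28% | 686 |
| 19% (illustrative only) | 20% | 1,059 |

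**Step 3: clustering.** Encounters per clinician m = 672/60 = 11.2. Design effect DE = 1 + (m − 1) × ICC = 1 + 10.2 × ICC. The ICCs are assumptions. Power is for p0 = 0.27%, the rate that reproduces 168.

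| Assumed ICC | DE | Effective n (168/DE) | Power |
|---|---|---|---|
| 0.01 | 1.10 | 152 | 76% |
| 0.05 | 1.51 | 111 | 62% |
| 0.10 | 2.02 | 83 | 50% |

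This takes equal numbers per clinician and counts the clinician level only. At p0 = 5% and ICC 0.05, power is 29% and the difference detectable with 80% power is 11.6 points.

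**Step 4: if the 1,400 patients of section 4.2 are analysed.** 1,400/4 = 350 per arm and m = 1,400/60 = 23.3. At ICC 0.05, DE = 1 + 22.3 × 0.05 = 2.12 and the effective n is 165.

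| Usual-care rate | Power, 350 per arm, no clustering | Power, assumed ICC 0.05 |
|---|---|---|
| 2% | 89% | 59% |
| 5% | 71% | 41% |
| 10% | 52% | 28% |

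**The case against.** A reader might infer that the 168 is simply an error, or that the trial lacks its stated power at every plausible usual-care rate. The documents support neither reading. The paragraph's inputs are missing, so the figure can be neither confirmed nor refuted from them. No section gives a usual-care rate of new SGLT2 inhibitor or MRA prescribing. The 19% belongs to a different endpoint covering GDMT classes, whose gain section 8.0 attributes to beta-blockers. The 22% and 39% are prevalences of current use. This part of the objection stands.

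The plan may also analyse more than 672. With 350 per arm and a 2% rate, power is 89% unclustered and 82% at an assumed ICC of 0.01. That stands too, but the 80% claim is made for 168 per arm, and at a rate of 5% or more the larger number does not restore it.

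The mixed model handles clustering and adjusts for the preintervention baseline, so the gap lies in the power paragraph and not in the analysis. Any gain in precision would have to be large: at a 5% rate, 168/435 = 39%, so the variance would have to fall by about 61% before any clustering penalty. Nothing in the plan supports a gain of that size.

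Finally, section 2.0 calls the effectiveness outcomes preliminary. It is therefore speculative to say that a null result will be taken as proof that nudges fail. The label does not excuse an unsupported power figure beside formal hypotheses.

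**Conclusion.** The concern holds in this form: the 80% figure is unsupported, and it is reached only under conditions that the plan neither states nor justifies. For independent patients and one arm against usual care, the usual-care rate must be about 0.3% two-sided, or 0.2% to 1.5% across the other variants that have a solution. At the two-sided rate there is no margin, so any positive ICC takes power below 80%.

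The root for the usual-care rate is arithmetic from the plan's own figures, given the choice of test. The power at each usual-care rate and the clustered results rest on assumed rates and ICCs; they show sensitivity and are not estimates for this trial. Whether the trial is in fact underpowered depends on the true rate, the ICC and whether 672 or 1,400 are analysed. The documents settle none of these.

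**What to change.** Replace the 80% statement in section 8.0.

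1. Estimate the usual-care rate of new prescribing and the clinician ICC from the prior 12-month data and the 3-month preintervention period, both already being extracted.
2. Before nudges start in month 10, restate the power for a 5-point increase, or the detectable difference. Do so for the stated contrast of each arm against usual care, two-sided, naming the test and using the design effect 1 + (m − 1) × ICC.
3. Base it on the number that will actually be analysed, and reconcile 168 patients per group, 672 encounters and 1,400 patients.
4. Power on the factorial margins (336 against 336) may be added as a supplement. It is a different contrast and does not replace the stated one.

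The cost is a rewritten paragraph and, most likely, a less favourable stated power. No patients are added.

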4.2 SUBJECT POPULATION

Study groups	Type of interaction	# screened for eligibility	# consent / chart review	# analysis	Comments
SAVAHCS prescribing clinicians (Primary Care, Cardiology)	Interview, focus group	Up to 100 (send invite to all Primary Care and Cardiology)	Up to 100 (consent for interview/focus group everyone accepting the invite)	Up to 100	ICF
	Nudge Interventions (alerts and emails)	N/A (all clinicians will be randomized)	Up to 100 (waiver of consent requested)	Up to 100	Waiver of consent
	Questionnaires	Up to 100	Up to 100 (waiver of documentation of consent requested)	Up to 100	Waiver of documentation consent
SAVAHCS Veteran and Family Advisory Panel	Focus group	Up to 20 (all panel members invited)	Up to 20	Up to 20	ICF – waiver of documentation (no recording)
SAVAHCS Patients with HF	Medical record review only	3000	1400	1400	HIPAA/PHI waiver

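### Power is calculated for 168 patients per arm, but the total and its feasibility are stated in encounters; if patients have repeat encounters, 672 encounters do not secure the stated 80%

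*Combined protocol and SAP*

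**What the plan says.** The power calculation in section 8.0 sets the effect first: "We anticipate a 5% absolute increase in new prescriptions (SGLT2 or MRA) per intervention arm, compared to usual care". It then sets the operating characteristics: "To detect this difference with an 80% power and alpha of 0.05". The per-arm requirement is in patients: "a sample size of 168 patients who are eligible to activate the alert are required in each treatment group". The same sentence gives the total in a different unit: "required in each treatment group, for a total study sample size of 672 patients encounters". The feasibility statement keeps the second unit: "We anticipate that we can achieve this number of patient encounters across the approximately sixty participating clinicians including any possible attrition".

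The data analysis text in section 8.0 says that outcomes are measured at patient level. It also says: "Models will include the preintervention baseline as a covariate and will use all patient visits until the conclusion of the data collection period". Patient visit number is a covariate, patient is a random effect, and the approach is described as handling repeated measures nested within clusters.

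Section 4.1 fixes the nudge period at 3 months. Under section 4.3 an alert goes out about two business days before an upcoming appointment, and under section 5.3 either a cardiology or a primary care appointment qualifies. No section limits a patient to one encounter. In section 4.2 the row for heart failure patients, marked "Medical record review only", lists 1400 for analysis.

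**The concern.** A patient random effect and a visit-number covariate are useful only if some patients have more than one visit. So the plan itself treats patients and encounters as different units, while the sample-size paragraph moves from one to the other at a rate of one to one.

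The unit matters because the powered outcome is a new prescription. A given patient can be newly started on a class only once, and section 5.3 requires that the patient is not already prescribed it. Repeat encounters therefore tend to come from patients who are still untreated, and they carry less independent information than the same number of new patients. As written, the plan never says that 168 distinct patients per arm are expected, which is the number that the 80% rests on. The count of 672 could be reached without the power attached to it.

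**Working it through.** **Inputs from section 8.0:** 168 patients per arm; total 672; difference 0.05; power 0.80; alpha 0.05.

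**Inputs not in the documents, so assumed:** a two-sided test (sidedness is not stated); the usual-care rate p0; the mean number of encounters per patient m; the within-patient correlation rho. The 22% and 39% in section 1.0 are rates of current use, not of new prescribing, so they do not supply p0.

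**Step 1, the total.** 4 x 168 = 672 exactly. The multiplication is right; only the unit changes.

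**Step 2, the plan's 168.** It cannot be reproduced from stated inputs, because p0 is missing. The p0 that returns it can be found from the pooled two-proportion formula

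n = [1.960 x sqrt(2 x pbar x (1 - pbar)) + 0.842 x sqrt(p0(1 - p0) + p1(1 - p1))]^2 / 0.05^2.

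With p0 = 0.0027, p1 = 0.0527 and pbar = 0.0277, the two terms are 0.4549 and 0.1930. Their sum is 0.6479, its square is 0.4198, and 0.4198 / 0.0025 = 167.9, so n = 168. The stated size therefore fits a two-sided test only at a usual-care rate near 0.3%.

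**Step 3, power with repeat encounters.** Hold encounters at 168 per arm. Effective n = 168 / (1 + (m - 1) x rho). With rho = 1 this is 168 / m, the number of distinct patients, and repeat visits add nothing. With rho = 0.5 they add part of their information. At p0 = 0.0027,

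power = Phi[(0.05 x sqrt(n) - 0.4549) / 0.2294].

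At n = 168: (0.6481 - 0.4549) / 0.2294 = 0.842, which gives 80.0% and reproduces the stated power.

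| Encounters per patient (m) | Distinct patients per arm | Power, rho = 1 (worst case) | Effective n, rho = 0.5 | Power, rho = 0.5 |
|---|---|---|---|---|
| 1 | 168 | 80% | 168 | 80% |
| 1.1 | 153 | 76% | 160 | 78% |
| 1.25 | 134 | 71% | 149 | 75% |
| 1.5 | 112 | 63% | 134 | 71% |
| 2 | 84 | 51% | 112 | 63% |

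**Step 4, sensitivity to the assumed test.** A one-sided test returns 167 per arm at a usual-care rate of 1%. On that basis, m = 1.25 gives 72% (rho = 1) and 76% (rho = 0.5), and m = 2 gives 55% and 65%. The pattern is the same.

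**Step 5, encounters needed for 672 distinct patients.** 672 x m: 840 at m = 1.25, 1008 at m = 1.5 and 1344 at m = 2.

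**The case against.** The strongest reply is that the shortfall is conditional. The phrase may be loose wording for 672 patients each seen at an eligible encounter, since the same sentence says 168 patients. Nor is 672 a cap or a stopping point: the nudge period is a fixed 3 months, all clinicians are randomised, and the dataset is every eligible patient on the dashboard. The 1400 patients in section 4.2 would be 350 per arm if split evenly, well above 168. All of this stands. It means that a deficit is not shown, but it does not tell the reader how many eligible patients will be seen in the nudge period, and section 8.0 does not say either.

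Two stronger readings are tempting and should not be drawn. A reader might infer that 1400 contradicts 672. It does not: 672 is the minimum for power, and 1400 is the number of patients planned for record review and analysis. The documents simply do not say how many of the 1400 are eligible and seen in the window. A reader might also infer that the correction needs no further patients. That is unsupported until the distinct patients are counted.

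It is also fair to say that a second visit is another chance to prescribe and that the mixed model uses it. That is why the rho = 1 column is labelled a worst case. Finally, the 80% is itself unverified: with 168 distinct patients per arm and no repeats, power would be about 41% at a 5% usual-care rate and 28% at 10%. The missing usual-care rate, and the absence of any allowance for clustering by clinician, may matter more. They are separate gaps, and neither repairs this one.

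**Conclusion.** The concern holds in conditional form. Section 8.0 attaches 80% power to 168 patients per arm but commits to, and judges feasible, only 672 encounters, in a plan that expects repeat visits. If any patient supplies more than one of those encounters, distinct patients average fewer than 168 per arm, and power is below the stated figure for any positive within-patient correlation.

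The size is illustrative only. It rests on three assumptions outside the documents: a usual-care rate near 0.3%, which is what the 80% requires with a two-sided test; the number of encounters per patient; and the within-patient correlation. On those terms power is about 71% to 75% at 1.25 encounters per patient and about 51% to 63% at 2, for correlations from 1 down to 0.5. It would be going too far to say that the trial will fall short, or that the sponsor's multiplication is wrong. What the documents show is that the stated size does not secure the stated power.

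**What to change.** In the power calculation of section 8.0:

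- State the target as 672 distinct patients, 168 per arm. This is the sample-size count only; the all-visits mixed model in the data analysis text stays unchanged.
- State feasibility as the number of distinct eligible patients expected to be seen by the approximately sixty clinicians during the 3-month nudge period, taken from one dashboard count.
- Say how many of the 1400 patients in section 4.2 that number represents.
- Restate power at that number, giving the assumed usual-care rate of new prescriptions.

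The cost is one dashboard query and a rewritten paragraph. The downside is that the restated power may be less favourable than 80%. Whether more encounters are needed than the 672 now stated depends on the count.
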